7.2. Laboratory Evaluations

Laboratory data collected during the study will be analyzed and summarized using both quantitative and qualitative methods. The analysis will be based on values reported in conventional units. When values are below the LOQ, they will be listed as such, and the closest imputed value will be used for the purpose of calculating summary statistics as specified in Section 3.7. Hemolyzed test results will not be included in the analysis, but they will be listed in by-participant laboratory listings.

Summaries of laboratory data will be provided for the Safety Analysis Set, and will include laboratory data collected in TE period defined at the beginning of Section 7.

A by-participant listing for laboratory test results will be provided by participant ID number and time point [visit] in chronological order for hematology, serum chemistry, and urinalysis separately. Values falling outside of the relevant reference range and/or having a severity grade of 1 or higher will be flagged in the data listings, as appropriate.

No formal statistical testing is planned.

7.2.1. Summaries of Numeric Laboratory Results

Descriptive statistics will be provided by treatment group for selected laboratory test as follows:

- Baseline values
- Values at each postbaseline visit
- Change from baseline at each postbaseline visit

A baseline laboratory value will be defined as the last measurement obtained on or prior to the date/time of first dose of study drug for treatment group 1, or the Study Day 1 for treatment group 3. Change from baseline to a postbaseline visit will be defined as the visit value minus the baseline value. The mean, median, Q1, Q3, minimum, and maximum values will be displayed to the reported number of digits; SD values will be displayed to the reported number of digits plus 1.

In the case of multiple values in an analysis window, data will be selected for analysis as described in Section 3.8.2.

Median (Q1, Q3) of the change from baseline values of Creatinine (mg/dL) and Glomerular Filtration Rate (mL/min/1.73m²) will be plotted by treatment group and by visit.

7.2.2. Graded Laboratory Values

The DAIDS Table for Grading the Severity of Adult and Pediatric Adverse Events, Version 2.1 dated July 2017, will be used to assign toxicity grades (0 to 4) to laboratory results for analysis. Grade 0 includes all values that do not meet the criteria for an abnormality of at least Grade 1. For laboratory tests with criteria for both increased and decreased levels, analyses for each direction (ie, increased, decreased) will be presented separately.

7.2.2.1. Treatment-Emergent Laboratory Abnormalities

Treatment-emergent laboratory abnormalities in randomized phase are defined as values that increase at least 1 toxicity grade from baseline at any postbaseline visit during the TE period defined at the beginning of Section 7.

If the relevant baseline laboratory value is missing, any abnormality of at least Grade 1 observed at any postbaseline visit will be considered treatment emergent.

7.2.2.2. Treatment-Emergent Marked Laboratory Abnormalities

TE marked laboratory abnormalities in randomized phase are defined as values that increase from baseline by at least 3 toxicity grades at any postbaseline time point during the TE period defined at the beginning of Section 7. If the relevant baseline laboratory value is missing, any Grade 3 or 4 values observed within the timeframe specified above will be considered TE marked abnormalities.

7.2.2.3. Summaries of Laboratory Abnormalities

Laboratory data that are categorical will be summarized using the number and percentage of participants in the study with the given response at baseline and each scheduled postbaseline visit.

The following summaries (number and percentage of participants) for treatment-emergent laboratory abnormalities will be provided by lab test and treatment group; participants will be categorized according to the most severe postbaseline abnormality grade for a given lab test:

- Graded laboratory abnormalities
- Grade 3 or 4 laboratory abnormalities
- Treatment-Emergent Marked Laboratory Abnormalities

For all summaries of laboratory abnormalities, the denominator is the number of participants with nonmissing postbaseline values during the TE period defined at the beginning of Section 7.

A by-participant listing of treatment-emergent laboratory abnormalities, treatment-emergent Grade 3 or 4 laboratory abnormalities, and treatment-emergent marked laboratory abnormalities, respectively, will be provided by participant ID number and visit in chronological order. This listing will include all test results that were collected throughout the study for the lab test of interest, with all applicable severity grades and abnormal flags displayed.

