3.1.1. Randomized Phase

Treatment Group 1

Participants in Treatment Group 1 will receive the long-acting regimen consisting of LEN, GS-5423, and GS-2872.

Participants will discontinue their baseline oral ART following administration of the complete study drugs on Day 1 (SC LEN 927 mg, oral LEN 600 mg, and IV infusions of GS-5423 and GS-2872), and will self-administer oral LEN 600 mg at home on Day 2. Participants will also receive study drug (SC LEN and IV infusion of GS-5423 and GS-2872) at Week 26.

All participants in Treatment Group 1 will return to the study center for visits at Weeks 4, 12, 24, 26, 38, 50, and 52.

Treatment Group 3

Participants in Treatment Group 3 will continue their baseline oral ART through Week 52. After Day 1, participants in Treatment Group 3 will return to the study center for visits at Weeks 12, 26, 38, 50, and 52.

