1.2.1. Randomized Phase

Participants in Treatment Group 1 will receive the long-acting regimen consisting of LEN, GS-5423, and GS-2872.

Participants will discontinue their baseline oral ART following administration of the complete study drugs on Day 1 (SC LEN 927 mg, oral LEN 600 mg, and IV infusions of GS-5423 and GS-2872), and will self-administer oral LEN 600 mg at home on Day 2. Participants will also receive study drug (SC LEN and IV infusion of GS-5423 and GS-2872) at Week 26.

All participants in Treatment Group 1 will return to the study center for visits at Weeks 4, 12, 24, 26, 38, 50, and 52.

Participants in Treatment Group 3 will continue their baseline oral ART through Week 52. After Day 1, participants in Treatment Group 3 will return to the study center for visits at Weeks 12, 26, 38, 50, and 52.

Duration of treatment in the Randomized Phase is 52 weeks.

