7. SAFETY ANALYSES

Analysis of safety data will be conducted on the Safety Analysis Set for randomized phase, unless otherwise specified in the following sections.

For randomized phase, the treatment-emergent (TE) period is defined as follows:

For treatment group 1 participants who receive any long acting LEN, TAB and ZAB, the TE period is the time period from the first dose date of study drug in the randomized phase up to and including the last study date (randomized phase) (Section 3.8.1). For participants who do not receive any injection or infusion but only receive oral LEN and permanently discontinued study drug, the TE period is the time period from the first dose date of study drug in the randomized phase up to and including 60 days after the last dose of the oral LEN.

For treatment group 3 participants, the TE period is the time period from the first dose date of study drug for the randomized phase up to and including study day 1(extension phase) for participants who enter extension phase or up to and including 30 days after the last dose date of randomized phase for the participants who do not enter extension phase.

In general, safety data during the TE period will be summarized, unless otherwise specified.

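### The worst-grade laboratory table sets five scheduled draws in Group 1 against four in Group 3, with longer follow-up in Group 1 outside the extension, so ascertainment leans modestly toward Group 1

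*SAP*

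**What the plan says.** SAP Section 7.2.2.1 defines a treatment-emergent laboratory abnormality by "values that increase at least 1 toxicity grade from baseline at any postbaseline visit during the TE period". Section 7.2.2.3 reduces each participant to one result per test: "participants will be categorized according to the most severe postbaseline abnormality grade for a given lab test". The tables (any grade, Grade 3 or 4, marked) are by treatment group. Anyone with a nonmissing post-baseline value in the treatment-emergent period is in the denominator.

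The visit schedules differ. Protocol Section 3.1.1 says "All participants in Treatment Group 1 will return to the study center for visits at Weeks 4, 12, 24, 26, 38, 50, and 52", while "participants in Treatment Group 3 will return to the study center for visits at Weeks 12, 26, 38, 50, and 52". The procedure tables place no chemistry, hematology or urinalysis at Weeks 24 and 50, and SAP Table 3-3 marks Week 4 as not applicable for Group 3.

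The end of the treatment-emergent period (SAP Section 7, with the dates in Section 3.8.1) depends on the path taken:

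- Extension entrants, either group: extension Day 1.
- Group 1 with any injection or infusion, not entering the extension: the last study date, which includes post-study-drug visits. Protocol Table 1 schedules safety laboratory tests at post-study-drug Days 30, 90 and 180.
- Group 1 with oral lenacapavir only: 60 days after the last oral dose.
- Group 3 not entering the extension: "up to and including 30 days after the last dose date of randomized phase for the participants who do not enter extension phase".

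**The concern.** A worst-ever grade depends on how often one looks. Each further draw can raise a participant's worst grade but cannot lower it, and the denominator does not account for the number of draws. With one more scheduled draw in Group 1, and a longer period for those outside the extension, equal true risk does not give equal expected percentages.

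Evaluating the safety and tolerability of the two groups is a secondary objective. No test of laboratory data is planned, so readers will judge from the percentages side by side. The lean has the same direction for every test drawn on this schedule. The plan has no version of the table with equal ascertainment.

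**Working it through.** **The plan's own figure.** The only numerical safety statement (Protocol Section 8.11, SAP Section 1.3) is the chance of at least one event at 5% incidence, 1 − (1 − p)^n. For n = 50, 1 − 0.95^50 = 92.3%. For n = 25, 1 − 0.95^25 = 72.3%. Both reproduce. The same form, with draws in place of participants, is used below.

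**Inputs.** Scheduled post-baseline draws: k = 5 in Group 1 and k = 4 in Group 3 (procedure tables and SAP Table 3-3). The documents do not give the per-draw chance p of a new graded abnormality, the within-person correlation ρ, or the share f not entering the extension. All three are assumptions here, with p equal in both groups.

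**Step 1: independent draws, Week 4 effect alone.** P(at least one) = 1 − (1 − p)^k.

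| p | Group 1 (k = 5) | Group 3 (k = 4) | Gap, points |
|---|---|---|---|
| 1% | 4.9% | 3.9% | 1.0 |
| 2% | 9.6% | 7.8% | 1.8 |
| 5% | 22.6% | 18.5% | 4.1 |
| 10% | 41.0% | 34.4% | 6.6 |

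The ratio is 1.22 at p = 5%. It cannot exceed 5/4 from this source.

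**Step 2: correlated draws.** Repeated values in one person are not independent. With a beta-binomial model, A = p(1 − ρ)/ρ and B = (1 − p)(1 − ρ)/ρ, and the chance of no abnormality in k draws is the product over i = 0 to k − 1 of (B + i)/(A + B + i). At p = 5%:

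- ρ = 0.3: 14.4% against 12.7%, a gap of 1.6 points before rounding of the two percentages.
- ρ = 0.6: 9.6% against 8.9%, a gap of 0.7 points.

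**Step 3: the longer Group 1 period.** Suppose a share f of each group does not enter the extension. Give those in Group 1 three further draws (8 in all) and those in Group 3 one (5 in all). With p = 5% and independent draws:

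- Group 1 = (1 − f)(1 − 0.95^5) + f(1 − 0.95^8)
- Group 3 = (1 − f)(1 − 0.95^4) + f(1 − 0.95^5)

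The gap moves from 4.1 points to 4.4 (f = 5%), 4.8 (f = 10%) or 5.5 (f = 20%). This is generous, because it assumes that each such participant has every scheduled draw and then all the later ones.

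**Step 4: matched draws.** With k = 4 in both groups, p = 5% and independence give 18.5% against 18.5%.

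**The case against.** Five arguments can be made for leaving the plan alone.

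- **The longer Group 1 period is deliberate.** Protocol Section 8.6.3 gives the groups different rules, and the SAP refers to prolonged exposure after the last long-acting dose. A 30-day cut could discard values taken while drug is still present. This stands, and it is why the main table should not be replaced.
- **The lean is small against the noise.** One Group 3 participant is 1/25 = 4 points. At p = 5% with independent draws, the standard error of the difference is √(0.226 × 0.774/50 + 0.185 × 0.815/25), about 9.8 points. The study is not powered for treatment comparison. This also stands for any single test, although noise has no fixed direction and the lean does.
- **The information is not lost.** Numeric values are summarized by visit, and the listings show all results with their grades. Week 4 abnormalities can be found there. But no planned table gives the incidence of graded abnormalities on matched draws.
- **Filtering on the SAP windows would bring in a new imbalance.** In Table 3-3 the Week 12 window starts at Day 57 in Group 1 and Day 2 in Group 3. This is correct, so the matched table needs a common start day.
- **Leaving out Week 4 could hide early toxicity.** This would be a fair objection to a replacement table. It does not apply to an added one.

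A reader might infer from the protocol's wording, which sets no end date for Group 1, that its window is open-ended throughout. The SAP does not support this: extension entrants in both groups stop at the same point, and Group 1 participants with oral lenacapavir only are capped at 60 days.

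**Conclusion.** The ascertainment is unequal. Group 1 has five scheduled draws against four, and among participants outside the extension its counting period is longer. At equal true per-draw risk, the expected proportion with an abnormality is modestly higher in Group 1.

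The size rests on assumptions, since the documents give no per-draw rate. For Week 4 alone it is 4.1 points at 5% per draw with independent draws, and about 1 to 2 points at 1% to 2% per draw or at 5% with correlation 0.3. It is under 1 point at 5% with correlation 0.6. The window difference adds to this only for those not entering the extension.

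A reader might go further and infer that Group 1 must show more abnormalities by construction, or that a specific false excess can be read into the table. Neither follows. Only the expected value shifts, and it shifts less when abnormalities persist within a person. A single data set of 50 and 25 could show the reverse. Eight draws for a typical Group 1 participant is also not supported. Under Protocol Section 6.3.11.1, a participant who stops early but attends scheduled visits for 52 weeks from the last dosing visit needs no further follow-up. For other early stoppers, post-drug visits overlap the remaining schedule in time.

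**What to change.** Keep the planned all-data treatment-emergent table as the main laboratory safety summary. Add one supplementary between-group table (any grade, Grade 3 or 4, marked):

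- Take the worst grade over the shared scheduled draws at Weeks 12, 26, 38 and 52 only.
- Use the same day range in both groups. For example, start at Day 57 in both, so that Group 3 does not start at Day 2.
- Apply the same Week 52 cut-off to both groups. Table 3-3 already has a common upper limit: Day 413 or extension Day 1, whichever is earlier.
- Show Group 1 abnormalities at Week 4 and at post-study-drug visits in separate rows.
- State the scheduled draws per group (5 and 4) in a footnote to the main table.

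Protocol Section 1.4.1.2 already reports Week 52 virologic results, so the table should be labelled as supplementary and as an addition to the plan.

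The cost is SAP wording, one filter and one extra table, with no new data. The supplementary table leaves out early values, but these stay in the main table and the listings.

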7.3. Body Weight and Vital Signs

Descriptive statistics will be provided by treatment group for body weight, BMI and vital signs as follows:

- Baseline value
- Values at each postbaseline visit
- Change from baseline at each postbaseline visit

A baseline value will be defined as the last available value collected on or prior to the first dose date of study drug. Change from baseline to a postbaseline visit will be defined as the postbaseline value minus the baseline value.

In the case of multiple values in an analysis window, data will be selected for analysis as described in Section 3.8.3. No formal statistical testing is planned.

A by-participant listing of vital signs will be provided by participant ID number and visit in chronological order. Body weight, height, and BMI will be included in the vital signs listing, if space permits. If not, they will be provided separately.

7.4. Prior and Concomitant Medications

Medications collected at screening and during the study will be coded using the current version of the World Health Organization (WHO) Drug dictionary. The WHO preferred name and drug code will be attached to the clinical database.

7.4.1. Nonstudy Drug Antiretroviral Medications

Any nonstudy drug ARV medications used prior to, during, or after the study (if collected) will be listed. No inferential statistics will be provided.

Antiretroviral medications at baseline will be summarized by ARV category and drug name. Antiretroviral medications at baseline are defined as the ARV medications taken on or up to 2 day prior to first dose date of study drug.

7.4.2. Prior and Concomitant Non-ARV Medications

Concomitant non-ARV medications are defined as non-ARV medications taken while a participant took study drug. Use of concomitant medications from Study Day 1 (randomized phase) up to the last exposure date (randomized phase) will be summarized (number and percentage of participants) by treatment group, and by preferred name. Multiple drug use (by preferred name) will be counted only once per participant. The summary will be sorted alphabetically by preferred drug name. For drugs with the same frequency, sorting will be done alphabetically.

If the start or stop date of non-ARV medications is incomplete, the month and year (or year alone, if month is not recorded) of the start or stop date will be used to determine whether the non-ARVs are concomitant or not. The medication is concomitant if the month and year of the start or stop (or year of the start or stop, if month is not recorded) of the medication does not meet either of the following criteria:

The month and year of start of the medication is after the last exposure date.

The month and year of stop of the medication is before the first dose date of study drug

If the start and stop date of non-ARV medications are complete, the start date is not after last exposure date and the stop date is not before first dose date, or the non-ARV medications are marked as ongoing and start date is on or before last exposure date, the non-ARV medications are concomitant.

Summaries of non-ARV concomitant medications will be based on the Safety Analysis Set. No formal statistical testing is planned. A by-participant listing for all non-ARV concomitant medications including prior medication will be listed and sorted by participant ID number and administration date in chronological order.

7.5. Electrocardiogram Results

The investigators' assessment of ECG results are collected.

A shift table of the investigators' assessment of ECG results at each scheduled postbaseline visit compared with baseline values will be presented by treatment group using the following categories: normal; abnormal, not clinically significant; abnormal, clinically significant; or missing. The number and percentage of participants in each cross-classification group of the shift table will be presented. Participants with a missing value at baseline or postbaseline will not be included in the denominator for percentage calculation. No inferential statistics will be provided.

A by-participant listing for ECG assessment results will be provided by participant ID number and visits in chronological order.

7.6. Other Safety Measures

A data listing will be provided for participants experiencing pregnancy during the study.

[figure not shown]
7.7. Changes from Protocol-Specified Safety Analyses

No change from protocol-specified safety analyses is planned.

8. PHARMACOKINETIC EVALUATION/ANALYSIS

8.1. PK Sample Collection

Blood sample for the determination of plasma LEN and serum GS-5423 and GS-2872 concentrations will be collected in all participants at scheduled time points.

8.2. PK Analyses Related to PK Sampling

8.2.1. PK Concentration

Individual participant concentration from serum PK samples of GS-5423 and GS-2872, as well as plasma PK samples of LEN will be determined using validated bioanalytical assays.

8.2.2. PK Parameters

PK parameters will be estimated using Phoenix WinNonlin[®] software using standard noncompartmental methods. The linear up/log down rule will be used in conjunction with the appropriate noncompartmental model, with input values for dose level, dosing time, PK concentration, and corresponding real-time values, based on drug dosing times whenever possible.

All predose sample times before time-zero will be converted to zero for the calculation of PK parameters.

For area under the curve (AUC), samples below the limit of quantitation (BLQ) of the bioanalytical assays occurring prior to the achievement of the first quantifiable concentration will be assigned a concentration value of zero to prevent overestimation of the initial AUC. Samples that are BLQ at all other time points will be treated as missing data in WinNonlin. The nominal time point for a key event (eg, urine collection) or dosing interval (τ) may be used to permit direct calculation of AUC over specific time intervals. The appropriateness of this approach will be assessed by the PK scientist on a profile-by-profile basis.

Pharmacokinetic parameters such as AUC_{inf} , λ_z and $t_{1/2}$ are dependent on an accurate estimation of the terminal elimination phase of drug. The appropriateness of calculating these parameters will be evaluated upon inspection of PK data on a profile-by-profile basis by the PK scientist.

The analytes and parameters presented in Table 8-1 will be used to evaluate the PK objectives of the study (as applicable).

Table 8-1. Pharmacokinetic Parameters for Each Analyte

Analysis Set	Analyte	Sample Matrix	Parameters
LEN PK Analysis Set	LEN	Plasma	Day 1 Dosing*: C _{max} , C _{maxday1} , T _{max} , T _{maxday1} , C _{trough} ; Week 26 Dosing: C _{trough}
GS-5423 PK Analysis Set	GS-5423	Serum	Day 1 Dosing: AUC _{tau} , C _{trough} , C _{max} , t _{1/2} , T _{max} ; Week 26 Dosing: AUC _{tau} , C _{trough} , C _{max} , T _{max}
GS-2872 PK Analysis Set	GS-2872	Serum	Day 1 Dosing: AUC _{tau} , C _{trough} , C _{max} , t _{1/2} , T _{max} ; Week 26 Dosing: AUC _{tau} , C _{trough} , C _{max} , T _{max}

* C_{maxday1} and T_{maxday1} are derived using LEN PK data from Day 1.

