1.4.1.2. Extension Phase

During the extension phase of the study, participants will receive 2550 mg CCI of both GS-5423 and GS-2872 administered IV in combination with LEN every 26 weeks. The dose selection for GS-5423 and GS-2872 in the extension phase is based on analysis of Week 52 data from the randomized phase of this study (GS-US-536-5939).

In the randomization phase, both GS-5423 and GS-2872 were evaluated at 2550 mg every 6 months, administered IV in combination with LEN. At Week 26 and Week 52, 1 and 3 participants receiving LEN, teropavimad (TAB), and znlirvimab (ZAB), respectively, had HIV-1 RNA $50 \geq$ copies/mL, and none of the participants who remained on a stable baseline regimen had HIV-1 RNA ≥ 50 copies/mL by snapshot algorithm.

Updated population pharmacokinetic (PopPK) models were developed for TAB and ZAB using data from the Phase 1b and Phase 2 (up to Week 52) studies to inform dose selection for extension phase evaluation of TAB and ZAB in combination with LEN. The PopPK model identified a statistically significant relationship between body weight and PK parameters for both TAB and ZAB, described by allometric scaling, resulting in a trend towards lower exposures in participants with higher body weight. Among the 3 participants with VF through Week 52 in the Phase 2 study, all weighed over 100 kg and generally had exposures below the median for both TAB and ZAB or LEN (Figure 2). Although the number of virologic failures through Week 52 in the Phase 2 study was limited (N = 3) and a definitive association between lower exposure and reduced efficacy cannot be established from Phase 2 Week 52 data, alternative dosing options for both TAB and ZAB to mitigate potential risk in higher-weight individuals were evaluated.

Model-based simulations of TAB and ZAB exposures (AUC , C_{max} , and C_{trough}) were conducted to assess the relationship between body weight and drug exposures, based on the body weight distribution of pooled historical Phase 3 studies in the virologically suppressed PWH population.

CCI

CCI

[figure not shown]

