4.3.3. Adherence to Study Drug

The adherence to SC LEN, IV infusion TAB and/or ZAB will be assessed by adherence to the projected injection/infusion interval, which is 26 weeks (182 days) between 2 adjacent injection/infusion visits. The number of days from the projected injection/infusion visit date will be calculated for each injection/infusion visit (excluding the 1st injection visit) as the injection/infusion visit date minus the previous injection/infusion visit date plus 1 day minus 182 days. The number of days from the projected injection visit date will be classified into the following categories:

- < - 14 days
- -14 to -8 days
- -7 to -3 days
- \pm 2 days
- 3 to 7 days
- 8 to 14 days
- > 14 days

The number and percentage of participants in each category will be summarized for treatment group 1 for the injection/infusion visits of interest.

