8.3.2. Statistical Analysis of PK Parameters

Individual estimates of pharmacokinetic parameters of LEN, GS-5423, and GS-2872 will be listed and summarized using descriptive statistics by treatment periods (Day 0 to Week 26, and Week 26 to Week 52) (eg, sample size, arithmetic mean, coefficient of variation %, SD, 95% CI for the arithmetic mean, geometric mean, %CV, median, minimum, maximum, Q1, Q3, sample size of natural log-scale [LN], geometric mean, Geometric Coefficient of Variation [%GVC], 95% Confidence Interval for Geometric Mean [GCI], mean of LN, SD of LN).

PK parameters listed in Table 8-1 will be included in the following tables by treatment periods (as applicable).

- Individual estimates and summary statistics of plasma LEN PK parameters using the LEN PK Analysis Set
- Individual estimates and summary statistics of serum GS-5423 PK parameters using the GS-5423 PK Analysis Set
- Individual estimates and summary statistics of serum GS-2872 PK parameters using the GS-2872 PK Analysis Set

PK parameters could be unestimatable due to insufficient concentration data or may be estimated but marked for exclusion due to reasons such as the participant received an incorrect dose. In such cases, the PK parameters will be included in the listing (as not reported [NR] or the estimate values) but will be excluded from the summary statistics, with reasons for exclusion identified.

In addition, determination of half-life and corresponding correlation coefficient will be provided in the following listings by treatment periods:

- Individual data on determination of GS-5423 serum half-life and corresponding correlation coefficient using the GS-5423 PK Analysis Set
- Individual data on determination of GS-2872 serum half-life and corresponding correlation coefficient using the GS-2872 PK Analysis Set

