Visit Window (Days)			Within 28 Days of Screening Visit 2		± 3 Days			± 6 Days						± 6 Days				± 6 Days	
Serum PK samples (GS-5423 & GS-2872) ^{m, n}			X				X	X	X	X	X	X	X	X		X	X	X	X
Plasma PK sample for LEN ^{m, o}			X				X	X	X	X	X	X	X	X		X	X	X	X
																			
Randomization			X																
HIV Treatment Preference Questionnaire			X							X			X			X			
HIVDQoL			X							X			X			X			
HIVTSQs ^q			X				X			X			X			X			
HIVTSQc ^q										X									
LEN oral administration ^r			X	X															
LEN SC administration			X							X			X			X			
GS-5423 IV infusion administration ^s			X							X			X			X			

Study Procedure	Screening		Randomized Phase											Extension Phase ^b			ESDD ^c	Post Study Drug Follow up ^e	
	Visit 1	Visit 2 ^a	Day 1	Day 2 ^b	Day 8 ^b	Day 15 ^b	Wk 4	Wk 12	Wk 24	Wk 26	Wk 38	Wk 50	Wk 52	Wk 64, 90, 116, 142	Wk 76, 102, 128, 154	Wk 78, 104, 130, 156		PSD Day 30, 90, 180	PSD Day 270, 365
Visit Window (Days)			Within 28 Days of Screening Visit 2		± 3 Days			± 6 Days						± 6 Days				± 6 Days	
GS-2872 IV infusion administration ^s			X							X			X			X			

CCI

ADA = antidrug antibody; AE = adverse event; ARV = antiretroviral; bNAb = broadly neutralizing antibody; CD4 = clusters of differentiation 4; CD8 = clusters of differentiation 8; DNA = deoxyribonucleic acid; ECG = electrocardiogram; eGFR = estimated glomerular filtration rate; ESDD = early study drug discontinuation; ET = early termination; FSH = follicle-stimulating hormone; Gilead = Gilead Sciences; HBV = hepatitis B virus; HCV = hepatitis C virus; HIV = human immunodeficiency virus; HIV-1 = human immunodeficiency virus type 1; HIVDQoL = HIV-dependent quality of life; HIVTSQc = HIV Treatment Satisfaction Questionnaire change version; HIVTSQs = HIV Treatment Satisfaction Questionnaire status version; IV = intravenous; LEN = lenacapavir; PBMC = peripheral blood mononuclear cell; PK = pharmacokinetic(s); PSD = post study drug; RNA = ribonucleic acid; SC = subcutaneous; TSH = thyroid-stimulating hormone; Wk = week

a Screening Visit 2 will be performed once results of GS-5423 and GS-2872 sensitivity testing from Visit 1 are reviewed and participant is deemed eligible to proceed.

- b Refer to Section 6.3.11 for ESDD and post-ESDD 30-, 90-, 180-, 270-, and 365-day follow-up visits. Counsel participant regarding the importance of continuing a complete ARV therapy in accordance to standard of care, and refer participant to an appropriate HIV treatment facility.

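### Noncompartmental AUCtau for the two antibodies is biased upward more after the Week 26 dose than after Day 1, because the first sample after infusion comes at 12 weeks rather than 4, so the by-period summaries overstate accumulation

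*SAP*

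**What the plan says.** SAP 8.2.2 fixes the integration method: "The linear up/log down rule will be used in conjunction with the appropriate noncompartmental model". Table 8-1 in that section lists AUCtau for GS-5423 and for GS-2872 after the Day 1 dose, and again in the entry that begins "Week 26 Dosing: AUC". SAP 8.3.2 states that the parameters "will be listed and summarized using descriptive statistics by treatment periods (Day 0 to Week 26, and Week 26 to Week 52").

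The visit schedule is in Protocol 3.1.1: "All participants in Treatment Group 1 will return to the study center for visits at Weeks 4, 12, 24, 26, 38, 50, and 52". SAP Appendix 1, Table 13-1, places a serum antibody sample at Day 1 and at each of those visits, and none in the Day 2, 8 and 15 columns. Its footnote n, like Protocol 6.3.6.1, adds a predose and an end-of-infusion sample at Day 1 and Week 26 and a single sample at other visits. The dosing interval, per SAP 4.3.3, is one "which is 26 weeks (182 days) between 2 adjacent injection/infusion visits".

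Protocol 1.4.1.2 records a second source of exposure estimates: "Updated population pharmacokinetic (PopPK) models were developed for TAB and ZAB using data from the Phase 1b and Phase 2 (up to Week 52) studies".

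**The concern.** The two AUCtau values carry the same name and appear in adjacent summaries, but they rest on different designs. The first interval has end of infusion and then 4, 12, 24 and 26 weeks after dose. The second has end of infusion and then 12, 24 and 26 weeks. The missing 4-week point falls where an intravenous antibody profile bends most.

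PK of the antibodies is a secondary objective. A reader of the report will naturally set second-interval AUCtau against first-interval AUCtau to see whether exposure builds up or holds steady on dosing every 26 weeks. Part of any rise seen that way would come from the sampling times and not from the drug.

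**Working it through.** **The plan's own figure.** There is none. The documents state no AUC, half-life or accumulation ratio, so nothing can be reproduced and the kinetics below are assumptions.

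**Direction.** The log-down segment between samples C1 and C2, a time Δt apart, is (C1 − C2) / ln(C1/C2) × Δt. It is exact for a single exponential. The logarithm of a sum of two exponentials is convex, so a straight chord on the log scale lies above the curve. The segment is therefore too large, and more so over a longer gap that starts at the peak. Under two-phase decline this direction does not depend on the parameter values.

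**Worked example.** Assumed: initial concentration 1 (arbitrary units); distribution share 0.4 with half-life 4 days; terminal share 0.6 with half-life 60 days; bolus approximation to the 30-minute infusion; interval 182 days (SAP 4.3.3). Rates are ln2/4 = 0.1733 and ln2/60 = 0.01155 per day.

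*First interval, samples at days 0, 28, 84, 168, 182*
- Concentrations at days 0, 28 and 84: 1, 0.4373, 0.2274.
- Days 0–28: (1 − 0.4373)/ln(1/0.4373) × 28 = 19.05; true area 16.64.
- Days 28–84: 17.97; true 17.92. Later segments are exact to the digits shown: 12.22 and 1.11.
- Total 50.36 against a true 47.90: bias +5.1%.

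*Second interval, samples at days 0, 84, 168, 182 after the dose*
- Carry-over multiplies the terminal term by 1 + exp(−0.01155 × 182) = 1.1221, so its share is 0.6733 and the peak is 1.0733.
- Concentration at day 84: 0.2551.
- Days 0–84: (1.0733 − 0.2551)/ln(1.0733/0.2551) × 84 = 47.84; true 38.51. Later segments: 13.72 and 1.25.
- Total 62.80 against a true 53.47: bias +17.4%.

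*Ratio of second to first:* true 53.47/47.90 = 1.116; as planned 62.80/50.36 = 1.247. The excess is 1.247/1.116 − 1 = 11.7%.

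**Range.** The same calculation, with 30-minute infusions, over 60 combinations (distribution share 0.2 to 0.6, distribution half-life 1 to 7 days, terminal half-life 40 to 80 days):

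| Quantity | Range | Median |
|---|---|---|
| First-interval bias | +1% to +23% | +6% |
| Second-interval bias | +5% to +57% | +18% |
| True ratio | 1.03 to 1.21 | 1.12 |
| Ratio as planned | 1.09 to 1.43 | 1.25 |
| Overstatement of the ratio | 4% to 28% | 12% |

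With a single exponential both biases are zero.

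**Is the log rule to blame?** No. A plain linear trapezoid on the same samples inflates the second interval by 11% to 117%. The sampling gap is the cause.

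**Matched times.** If the first interval is recomputed without its Week 4 sample, the ratio lies within −4.6% to −0.2% of the truth over the same grid. First-interval AUCtau itself is then inflated by 6% to 59%. In a compartmental case with CL 0.08 L/day, V1 3.5 L, Q 0.5 L/day and V2 3.0 L, the biases on the full schedule are +10.3% and +28.7%. The true ratio is 1.11, the planned ratio 1.30 and the matched ratio 1.09, and the matched first-interval bias is about +32%.

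**The case against.** The case for leaving the plan alone has real force.

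- **No between-period contrast is planned.** SAP 8.3.2 and Protocol 8.8 plan descriptive summaries, with no accumulation ratio or test. Trough concentration is a named secondary endpoint and Table 8-1 gives Ctrough for both intervals, so accumulation can be judged without AUCtau. This stands. The harm comes only through how adjacent summaries are read.
- **Dose selection did not depend on it.** Protocol 1.4.1.2 bases the extension-phase dose evaluation on population PK models. This stands, and it rules out an inference that the trapezoid compromised that decision.
- **The size is assumed.** A reader might take one set of antibody kinetics (CL 0.06 to 0.12 L/day, V1 3.0 to 3.5 L, Q 0.3 to 0.8 L/day, V2 2 to 4 L) and infer that Week 26 AUCtau is inflated by 22% to 42%. Those values imply a strong distribution phase, roughly 38% to 68% of the initial concentration where checked. Nothing in the documents supports preferring them, and weaker distribution gives much less bias.
- **Masked loss of exposure.** A reader might also infer that the bias could hide a fall in exposure caused by antidrug antibodies. SAP 9.2 examines that question with individual concentration–time plots and listings, not AUCtau, and a lower second-dose exposure would show in the Week 38, 50 and 52 concentrations.
- **PK scientist discretion.** The profile-by-profile judgement in SAP 8.2.2 covers the use of nominal times and the terminal-phase parameters. It does not address this gap, so this objection fails.
- **Redaction.** Sampling for the optional PK substudy is blacked out, so extra samples there cannot be checked. No visit column lies between Weeks 26 and 38, and the substudy is optional, so the gap stands for the main PK sets.

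**Conclusion.** The concern holds in a limited form. As written, the SAP will report a second-interval AUCtau that is biased upward and not comparable with the first-interval value, which is biased upward by less. Under the assumed kinetics the apparent second-to-first ratio is overstated by 4% to 28%, median 12%. The direction requires only that decline has two phases; the size cannot be taken from the documents.

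It would be too strong to say that the accumulation seen is false. With a terminal half-life of 40 to 80 days some accumulation is real (true ratio 1.03 to 1.21), and the artefact adds to it. Nor is the log-down rule an error. The primary endpoint, Cmax, Ctrough and the population PK work are untouched. The correction is still worth making because it uses existing data and AUCtau is one of the parameters that Table 8-1 assigns to the PK objectives.

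**What to change.** In SAP 8.2.2 and Table 8-1:

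1. Report AUCtau for both intervals from the existing TAB and ZAB population PK models, and make these the basis for any statement that compares periods.
2. If noncompartmental AUCtau is kept, retain the full-schedule Day 1 value as the estimate for that interval. Add a sensitivity version of Day 1 AUCtau on matched times (end of infusion, then 12, 24 and 26 weeks after dose), used only for the Day 1 versus Week 26 comparison.
3. Footnote the tables: Week 26 AUCtau rests on sparse sampling, is biased upward, and must not be compared directly with full-schedule Day 1 AUCtau.

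The cost is SAP wording, one extra derivation and reliance on a model. Protocol 1.4.1.2 already reports Week 52 results, so the randomized-phase sampling cannot be changed, and none of these steps needs new samples. The matched Day 1 value is more inflated than the full-schedule one, so it is fit for the ratio and should not be quoted as an exposure.
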